### **Design and Methods**

Participants will be divided into two groups – experimental and control group.

The experimental group will spend two weeks wearing the Fitbit for as close to 24 hours each day (including during sleep), except when showering or charging the device. For the second week, participants will also use the Fitbit meditation app, Relax, to complete a 5-minute breathing meditation once a day, every day for one week. The Fitbit will measure physical activity and record physiological data. Following the two weeks, a subset of the experimental group will participate in semi-structured interviews to discuss their experience.

The control group will wear the Fitbit for 2 weeks, but will not complete any meditation. They will be offered the opportunity to participate in the meditation activities after the study is complete.

Participants will complete the HADS survey, MHC-SF survey, UMC Penn State Worry Questionnaire, and MAAS survey, at baseline and at the end of the second week of the program (please see attached for all surveys). They will also complete a pre-program survey at baseline and a post-program survey (including demographic information and experience with COVID-19) after the 2-week program (please see attached surveys). All surveys will be administered via email and completed via Qualtrics.

Additionally, a subset of participants will be invited to complete semi-structured interviews with the research team about their experience (please see attached for interview questions). Each interview will have 6 questions, but the total number of questions may vary depending on the follow-up questions prompted by the subjects' responses. The estimated time to complete the interview is 30 minutes.

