### **Statistical Analysis Plan (SAP)**

Survey data collected via Qualtrics (Provo, UT). Fitbit data downloaded from participants' Fitbit accounts into Microsoft Excel for analysis. Statistical analysis using R ([R Core Team, 2021](#), R Version 4.1.0, Vienna, Austria). Data combined across all three cohorts for all analysis. All data assessed for normality using the Shapiro-Wilk test, and  $p > 0.05$  for all samples. Fisher's exact test used to analyze categorical variables (race, class, sex), and t-tests used to analyze continuous variables (age, BMI) between control and treatment groups in demographic data. Paired t-tests used to compare baseline/post-study survey data and week 2/week 1 Fitbit data, and t-tests used to compare control and treatment groups at each time point. All values are reported as mean  $\pm$  standard deviation (SD). To examine the mean differences between groups, 95% confidence intervals (CI) were used ([Cumming, 2014](#)).

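### No planned between-arm test of the post-intervention value accounts for baseline or week 1, and no primary outcome or multiplicity rule says which result answers the trial's question

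*Combined protocol and SAP*

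**What the plan says.** The section Statistical Analysis Plan (SAP) gives two families of outcome test. Over time: "Paired t-tests used to compare baseline/post-study survey data and week 2/week 1 Fitbit data". Between arms: "t-tests used to compare control and treatment groups at each time point". It adds an interval statement: "To examine the mean differences between groups, 95% confidence intervals (CI) were used". It does not say whether those differences are in post-intervention values or in change, or whether they are adjusted for anything. It also does not say whether the paired tests are run within each arm or over both arms together.

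Design and Methods supplies the data. On the surveys: "Participants will complete the HADS survey, MHC-SF survey, UMC Penn State Worry Questionnaire, and MAAS survey", collected "at baseline and at the end of the second week of the program". Both arms wear the Fitbit for two weeks, and only the experimental arm meditates, in week 2 only. Week 1 is therefore a pre-intervention Fitbit value in both arms. On allocation the text says "Participants will be divided into two groups" and gives no method.

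No outcome or comparison is called primary. There is no multiplicity rule, no exploratory label and no alpha for the outcome tests. The only 0.05 in the SAP belongs to the normality check.

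**The concern.** The effect of meditation is a contrast between arms at the end of week 2, given where each arm started. Neither family of tests estimates that contrast while using the starting value.

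- **Experimental-arm paired test.** It ignores the control arm. Anything that moves both arms alike over the two weeks, including wearing a tracker, is counted as change in the meditating arm.
- **Post-only between-arm test.** It ignores the starting value. If the arms are comparable at the start, this only wastes precision. If they are not, it carries the starting difference into the result.

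These are problems of bias and precision. A separate problem is chance: several outcomes and two kinds of test are open to being read as an effect of meditation, and nothing fixes which one counts.

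**Working it through.** **The plan's own figure.** The Description section anticipates 20 participants, 10 per arm. No effect size, SD, power or alpha goes with it, so there is nothing to reproduce.

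**Inputs.** From the documents: 10 per arm, four surveys, and three Fitbit domains (heart rate, physical activity, sleep). Assumed, because the documents do not fix them: two-sided 0.05 per test, no meditation effect, pre-post correlation r of 0.5, 0.7 or 0.8, and outcomes scaled to SD 1.

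**1. Shared time trend, one outcome.** The change has SD √(2(1−r)), so a trend of δ gives a standardised change of δ/√(2(1−r)). The paired test then follows a noncentral t with 9 df and noncentrality √10 times that value.
- δ = 0.2, r = 0.5: 0.2/1.00 = 0.20; significant in 8.8% of trials.
- δ = 0.5, r = 0.8: 0.5/0.632 = 0.79; significant in 60.6% (60.1% by simulation).

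The range is about 9% to 60%. ANCOVA between arms stays at about 5%, because the trend cancels.

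**2. Baseline difference, one outcome.** Suppose the arms start 0.3 to 0.5 SD apart. The gap may persist in full or regress to r times its size.

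| Test, 10 per arm | Gap persists | Gap regresses |
|---|---|---|
| Post-only t-test | 10% to 19% | 6% to 14% |
| ANCOVA | 6% to 9% | 5% |
| Change score | 5% | 6% to 8% |

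Over both cases the post-only test errs in about 6% to 19% of trials and ANCOVA in 5% to 9%. Neither ANCOVA nor the change score is best in both columns.

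**3. Precision when arms are comparable.** Approximate half-width of the 95% CI for the arm difference:
- Post-only: 2.101 × √(2/10) = 0.94 SD.
- ANCOVA: 2.110 × √((1−r²) × 2/10) = 0.82, 0.67 and 0.57 SD for r = 0.5, 0.7 and 0.8.

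**4. Chance, several outcomes.** One score per survey and one metric per Fitbit domain gives 4 + 3 = 7 outcomes. This count is an assumption, since the SAP does not list them. Any p < 0.05 is counted, with no trend and no baseline gap.
- Independent tests: 1 − 0.95^7 = 30% and 1 − 0.95^14 = 51%.
- Simulated, with between-outcome correlation from 0.7 down to 0: about 18% to 30% for the 7 post-only between-arm tests, and 33% to 50% when the 7 experimental-arm paired tests are added.
- Seven ANCOVAs (r = 0.7) give about 19% to 30%, so adjustment for baseline does not lower this error.

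**5. Sensitivity to size.** The SAP says "Data combined across all three cohorts for all analysis". The documents do not settle whether 20 is the total or the number per cohort. At an assumed 30 per arm the rates in step 4 hardly change (18% to 30% and 32% to 51%). In step 2 the post-only test errs in 9% to 47% of trials and ANCOVA in 5% to 18%.

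**The case against.** The strongest reply has four parts.

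- **The arms are compared, with intervals.** True. If the arms are comparable at the start, each post-only t-test holds its 5% level and only precision is lost. The bias in step 2 needs arms that differ, and the allocation wording neither states nor rules out randomisation. This stands, and it is why step 2 is conditional.
- **ANCOVA is one choice among several.** Partly true. If a baseline gap persists in full, the change score holds 5% and ANCOVA does not; if the gap regresses, the order reverses. Both still beat a test that ignores the starting value or the other arm.
- **The sizes are mostly assumed.** True of the outcome count, alpha, correlations, trend and baseline gap, and of counting any p < 0.05 as a finding. The omissions themselves can be checked by reading and do not depend on these figures.
- **This is a small study, so multiplicity matters little.** The documents do not label the tests exploratory. If that is the intention, stating it is part of the remedy.

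**Conclusion.** The concern holds. No planned test isolates the week 2 meditation effect from both time and starting level, and nothing ranks the outcomes. The bias is up to about 60% false significance for the experimental-arm paired test (shared trend of 0.5 SD, r = 0.8) and up to about 19% for the post-only test (persisting gap of 0.5 SD). The chance error is about 18% to 30%, or 33% to 50% with the experimental-arm paired tests included. All of this assumes 10 per arm, two-sided 0.05 and no effect; the chance figures also assume 7 outcomes.

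A reader might infer more than the documents support:
- That no between-arm test touches the baseline or week 1 value. The SAP compares the arms on every occasion, including the first. What is missing is a test of the later value that accounts for the earlier one.
- That the confidence intervals are unadjusted. The SAP does not specify them.
- That every planned test belongs in the false-positive count, which would give far higher rates. Pre-intervention comparisons and control-arm paired tests cannot show a meditation effect.
- That allocation was not random. The text is silent on this.

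This should be changed, but it does not make the study unworkable.

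**What to change.** **Comparison.** For each outcome, state in advance one between-arm comparison with its 95% CI as the evidence of effect: ANCOVA of the end-of-study survey score on arm and baseline score, and of the week 2 Fitbit value on arm and week 1 value. Make no effect claim from within-arm or pre-intervention p-values.

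**Allocation.** State how participants were allocated. If it was not at random, add the between-arm comparison of change scores as a sensitivity analysis, because each method leaves bias where the other does not.

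**Multiplicity.** The SAP says "All data assessed for normality using the Shapiro-Wilk test" and reports the result, so first state whether outcome data had been seen when it was written. If they had, label all outcomes exploratory and report every test run. Only if they had not, name one primary outcome, test it once at two-sided 5%, and treat the rest as exploratory.

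**Cost.** SAP wording and one covariate (1 df) per outcome; no new data. Secondary outcomes lose their significance claim, and if data had been seen the trial gives up any confirmatory claim. Without random allocation, ANCOVA still leaves an error of up to about 9% at 10 per arm, or 18% at 30 per arm, for a persisting gap of 0.5 SD.
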